13.1 Assessments

See Table 1.

Table 1: Schedule of enrolment, interventions and assessments

Procedures							
				Treatment Pha	ase	Follow Up	
	Eligibility	Baseline	Month 1	Month 3	Month 6	Month 12	Month 13
MSU (central lab) *	x	x	x	x	x	x	
MSU (Local lab)			Sent to local lab	only if symptom	s of a UTI are pr	esent	
Eligibility assessment	x	X					
Informed consent	X	x					
Registration/contacts form	X	X					
Demographics	X	x					
Medical history	X	X					
Physical examination	X	X					
rUTI Impact questionnaire*	X	X	X	x	X	X	
UTI diary*			X	x	X	X	
EQ-5D-5L	X	X	X	X	X	X	

Service use questionnaire (SUQ)	X	x			X	x	
Perineal swab (central lab)	х	X			х	х	
eGFR	X	X	х	х	х	х	
LFTs	X	X	Х	х	х	х	
Randomisation	X	X					
Dispensing of trial drugs	X	X					
Adverse events			X	х	х	х	
Pregnancy reporting form			Х	х	х	х	
Adherence to intervention			Х	х	х	х	
Self Vs hospital							
administration of			x	х	x	х	
intravesical treatment					~		
Treatment Satisfaction Questionnaire					x	x	

GP or hospital records search		x	x	X	x	
DCE						Х

* Repeated at time of UTI.

X – denotes schedule to follow when a patient presents without symptoms of a UTI and no antibiotic treatment for a UTI in the previous 4-weeks. If this is the case, then the eligibility and baseline appointments can be combined.

NHS

13.1.1 Eligibility and baseline appointment

See Figure 2 for the trial procedures from eligibility assessments through to randomisation.

An initial eligibility check will be conducted where patients are asked whether they currently have symptoms of a UTI or have received antibiotic treatment for a UTI in the previous 4-weeks.

For those who answer 'no' to both the above questions and are eligible, they will be consented at the eligibility appointment. The MSU sample and perineal sample (for the central lab) will be collected. Bloods (local labs as per usual care processes) will be taken to determine eGFR and LFT levels. For patients who have eGFR data in their medical records that are within the previous 8 weeks, the clinician can choose to use these results, and not send a sample off for eGFR testing. The baseline data will then be collected as described in section 13.1.2.

The participant can then be randomised.

For participants randomised to the oral antibiotic arm, a prescription can be issued based on the eGFR results. If participant has eGFR results in their medical notes from within the last 8 weeks, the recruiting clinician can choose to use these results to assist with determining an antibiotic prescription. If eGFR results are not yet available from the bloods taken, the clinician will issue a prescription, letting the participant know that if the eGFR results indicate it, they may need to switch to another antibiotic and they will be contacted if this is the case. If the eGFR results indicate the participant is not suitable for any of the second line oral antibiotics, the participant will need to be withdrawn. If in an intravesical arm the site team will arrange an appointment with the participant for their first instillation at clinic.

For those patients who answer 'yes' to currently having symptoms of a UTI and/or have received antibiotic treatment for a UTI in the previous 4-weeks, the processes indicated in the red boxes of Figure 2 are to be followed. Those patients with current UTI symptoms will need to wait for the results of the local laboratory urine culture tests to come back to the site team. Patients with a positive culture will need to be prescribed antibiotics and following the antibiotic course wait for a further 4week wash out period before they can be asked back to clinic to a 'baseline' appointment to re-assess their eligibility, consent, complete sample collection and baseline data collection. Participants can then be randomised. For those in the oral antibiotics arm, the eGFR results will assist in determining

Canolfan

the antibiotic prescription (as described above). For those in the oral antibiotics arm, their prescription can be issued. For those in the intravesical arms, an appointment is booked for their first instillation.

For those patients who answer 'yes' to having antibiotic treatment for a UTI in the previous 4-weeks, they will need to wait a total of 4-weeks for a wash-out period before they can be invited back to clinic to re-assess their eligibility, consent, complete sample collection and baseline data collection. Participants can then be randomised. For those in the oral antibiotics arm, the eGFR results will assist in determining the antibiotic prescription (as described above). For those in the oral antibiotics arm, their prescription can be issued. For those in the intravesical arms, an appointment is booked for their first instillation.

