In the event a withdrawal form in not completed, it must be assumed that the participant withdraws from all aspects of the trial, and any unprocessed samples retained at the central laboratory must be disposed. However, retained samples can be processed for use in the trial if the participant have signed the optional statement in the consent form that allows the samples to be retained in the event the participant does not complete the withdrawal form.

NB: If a participant is withdrawn for medical reasons by a clinician, the withdrawal form need not be completed. However, confirmation would be needed that the participant agrees to their samples being retained and used as per original consent.

Any queries relating to potential withdrawal of a participant should be forwarded to [contact] for the attention of the trial manager.

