15.7 Inclusion in analysis

All eligible participants who have been randomised will be included in the primary intention-to-treat analysis regardless of their treatment adherence, discontinuation, and initiation of the subsequent treatment as described in the primary estimand Section 16.1 below. As part of sensitivity analyses, ineligible participants will be excluded from the analysis, and alternative analysis populations (as described in Section 16.1) will be used.

16 Analysis

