16.1 Main analysis

Descriptive statistics will be summarised using frequencies and percentages, means and standard deviations, or medians and interquartile ranges as appropriate. Recruitment, retention, and other trial processes (e.g. adherence to allocation) will be reported both overall, by arm, and disaggregated by site, menopausal status, previous UTI frequency, and previous type of failed treatment.

The primary analysis will be an intention to treat, including all randomised participants regardless of adherence or discontinuation of the initial treatment allocation or initiation of the subsequent treatment.

For the clinical-effectiveness primary outcome (rate of symptomatic, antibiotic-treated UTI, selfreported by participants from randomisation to the 6-month treatment period (verified from medical

Canolfan

records)), a Poisson/negative binomial regression model will be fitted to estimate incidence rate ratios, including fixed effects for allocation, covariate factors used in randomisation (prior frequency of UTI and menopausal status) and random effects to model heterogeneity between sites. Regression analysis results will be presented as point estimates with confidence intervals and p-values. The primary estimand for VESPER is below:

Primary clinical question: In women who fail first-line preventative treatment for rUTI, does the strategy to initially prescribe intravesical treatments result in a greater reduction in the rate of symptomatic UTIs over the subsequent 6 months compared to the current guideline-recommended second-line prophylactic antibiotic therapy?

The estimand is described by the following attributes:

- Population: women aged >16years with recurrent uncomplicated UTI who have failed firstline treatments requiring second-line prophylactic treatment and able to receive intravesical treatments and take second-line oral antibiotic prophylaxis.
- **Endpoint**: rate of symptomatic UTIs from randomisation to 6-months. •
- **Treatment condition**: The intravesical treatments and second-line oral antibiotic prophylaxis, regardless of adherence or discontinuation of the initial treatment allocation or initiation of the subsequent treatment (via re-randomisation) (treatment policy strategy);
- Remaining intercurrent events: Treatment adherence or discontinuation or initiation of the subsequent treatment are covered by previous attribute.

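### The protocol fixes its primary analysis set in two conflicting ways, and an eGFR withdrawal rule written only for the oral arm lets the narrower version exclude women according to allocation.

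*Protocol*

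**What the plan says.** **Analysis set.** Protocol section 15.7 (Inclusion in analysis) states: "All eligible participants who have been randomised will be included in the primary intention-to-treat analysis". Its next sentence states: "As part of sensitivity analyses, ineligible participants will be excluded from the analysis". Section 16.1 (Main analysis) states: "The primary analysis will be an intention to treat, including all randomised participants". Section 16.1 also sets a treatment-policy estimand and says women are analysed in the arm first allocated, using multiple imputation, whatever treatment they received and whether or not their outcome is available.

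**Order of events at baseline.** In section 13.1.1, bloods are taken, baseline data are collected and the woman can then be randomised. For the oral arm it adds: "If eGFR results are not yet available from the bloods taken, the clinician will issue a prescription". It continues that if the "eGFR results indicate the participant is not suitable for any of the second line oral antibiotics, the participant will need to be withdrawn". The sentence straight after turns to the other arms: "If in an intravesical arm the site team will arrange an appointment with the participant for their first instillation at clinic".

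**Eligibility.** Section 8.2 excludes women who cannot have intravesical treatment or cannot take second-line oral prophylaxis. That criterion applies before allocation, so it covers all three arms.

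**The concern.** An intention-to-treat comparison depends on an analysis set fixed by randomisation and not by anything learned or done afterwards in one arm. Here the protocol defines the primary set twice, and the two definitions differ for exactly one group: women randomised and later found ineligible.

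Section 13.1.1 describes how such women come to light, but only in the oral arm. An oral-arm woman whose eGFR returns after allocation and leaves no usable oral agent is withdrawn. A woman with the same result in an intravesical arm goes on to her first instillation, and nobody is asked to consider whether she could have taken oral prophylaxis. If the 15.7 wording is then followed literally, the first woman leaves the primary analysis and the second stays.

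At stake is the comparability of the control arm, which serves both first-stage comparisons and is the smallest arm (62, against 175 and 175). The trial is open label. If the choice between the two definitions is left until data have accrued, it could be made with outcomes in view.

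**Working it through.** There is no plan figure to reproduce; the check is a reading of the sections together, followed by an illustration of scale.

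**Step 1. Can both definitions of the primary set hold?**
- 15.7: eligible and randomised.
- 16.1: all randomised.
- 15.7, sensitivity analysis: ineligible women removed.

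Under the first definition the sensitivity analysis in 15.7 reproduces the primary set as far as eligibility goes. Under the second it is a real sensitivity analysis. So 15.7 is inconsistent with 16.1 and with its own next sentence.

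**Step 2. Does detection of ineligibility depend on arm?**

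| | Oral arm | Intravesical arms |
|---|---|---|
| Ineligible if unable to take oral prophylaxis (8.2) | yes | yes |
| eGFR measured at baseline (Table 1) | yes | yes |
| May be randomised before the result is known (13.1.1) | yes | yes |
| Result checked against all oral agents (13.1.1) | yes | not stated |
| Withdrawn if none is suitable (13.1.1) | yes | not stated |

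The criterion and the measurement are common to all arms; the action is not.

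**Step 3. Combine.** Under 16.1, the oral-arm woman stays in the analysis whatever 'withdrawn' means, with imputation if her outcome is missing. Under 15.7 as worded, she is dropped and her intravesical counterpart is kept.

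**Step 4. How many women?** Section 11.5 bars nitrofurantoin below 45 ml/min and halves trimethoprim below 30 ml/min. It gives no eGFR limit for amoxicillin or cefalexin, and section 6 leaves the list of oral agents open. On these rules eGFR alone does not rule out every agent; it would have to combine with other contraindications. The documents give no frequency.

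**Step 5. Scale, under assumptions.** Suppose a share f of oral-arm women is dropped, comparable women stay in the intravesical arms, and these women have m times the UTI rate of the others. The intravesical-to-oral rate ratio is then multiplied by (1 − f) + f × m. Neither f nor m is in the documents.
- f = 0: factor 1, no bias.
- One woman, f = 1/62 = 1.6%, m = 2: 0.984 + 0.032 = 1.016.
- f = 5%, m = 2: 0.95 + 0.10 = 1.05; a true ratio of 0.50 becomes 0.525.
- f = 5%, m = 3: 0.95 + 0.15 = 1.10; 0.50 becomes 0.55.
- f = 5%, m = 0.5: 0.95 + 0.025 = 0.975; the direction reverses.

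**Step 6. Power.** Inputs: 15% drop-out applied to 62 and 175 gives 62 × 0.85 = 52.7 and 175 × 0.85 = 148.75; rates 2 and 1 (section 15.3); dispersion k = 1 (assumed). SE = √[(1/2 + k)/n_oral + (1/1 + k)/n_iv], and power = Φ(ln 2/SE − 1.96).
- None lost: SE = √(1.5/52.7 + 2/148.75) = 0.205; power 92.3%.
- Three lost, n_oral = 59 × 0.85 = 50.15: SE = √(1.5/50.15 + 2/148.75) = 0.208; power 91.5%.

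If the rates in 15.3 are annual, so that the 6-month means are 1 and 0.5, the same calculation gives 82.0% falling to about 81%. In either case the loss is about one percentage point.

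**The case against.** The strongest reply is that the intended set can be recovered. Section 16.1 says all randomised women, its estimand is treatment policy, and the sensitivity analysis in 15.7 presupposes that ineligible women are in the primary set. On that view 'eligible' is one stray word. This stands as a statement of likely intent, and it is why the repair is small. It does not remove the contradiction: the section whose purpose is to define inclusion still says something else.

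Second, 'withdrawn' in 13.1.1 is not defined. Section 10.1 lists seven aspects of withdrawal, treatment being one, and section 9.5 keeps women who change treatment in follow-up and in the analysis as allocated. A reader might infer that 13.1.1 removes women from the analysis and so breaks intention to treat outright. The documents do not establish that: removal follows only if 13.1.1 is read with the 15.7 wording. Equally, nothing in 13.1.1 limits the withdrawal to treatment. By contrast, section 11.1 says expressly, for each arm, that women who stop for intolerance continue in the study.

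Third, few women are likely to be affected (Step 4). That stands, and it limits the size but not the principle.

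A reader might also infer that section 10.1 breaks intention to treat, because without a withdrawal form "it must be assumed that the participant withdraws from all aspects of the trial". The documents do not support that either. The rule concerns women who withdraw; data already collected are kept; a clinician's medical withdrawal needs no form; section 15.4 imputes incomplete follow-up; and women whose prophylaxis fails or is not tolerated have a re-randomisation route (sections 9.6.2 and 15.1). It is at most a missing-data risk, and no rate of missing forms is given from which to size it.

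**Conclusion.** The point holds in this form: 15.7 and 16.1 contradict each other on the primary analysis set, and the arm-specific step in 13.1.1 means that the 15.7 version can make exclusion depend on allocation, in the control arm, against the stated estimand. Both parts rest on the text alone.

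The protocol provides for an allocation-dependent exclusion if followed literally; that any woman would in fact be excluded is not shown. It depends on two readings: that the withdrawal sentence applies to the oral arm only, as its position implies, and that the 15.7 wording governs. The number affected is unknown and probably small. With illustrative shares of up to 5% and relative UTI rates of 0.5 to 3, the rate ratio moves by a factor of 0.975 to 1.10, and by none if no woman is affected. If the excluded women have higher UTI rates, a true intravesical benefit is understated. Power is barely touched. The reason to act is that the primary set should be unambiguous and independent of arm before data accrue.

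**What to change.** - **Section 15.7:** delete 'eligible', so that the primary set is all randomised participants as allocated, in line with 16.1. Keep the exclusion of ineligible women as a sensitivity analysis, and state that ineligibility is judged from baseline data, including baseline eGFR, by the same rule in all three arms. Table 1 already schedules baseline eGFR for everyone, so no new data are needed.
- **Section 13.1.1:** state that this withdrawal is from allocated treatment only, and that follow-up and records extraction continue unless the woman withdraws consent for them. Alternatively, require eGFR suitability to be confirmed before randomisation in all arms, using a new result or one from the previous 8 weeks as the section already allows.

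What treatment such a woman should then receive is a clinical matter and is not addressed here.

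**Cost:** a protocol amendment of a few words for the first change and one clause for the second. The alternative in 13.1.1 would add a few days' wait for women with no recent eGFR result; the wording change would not.

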13.1.2 Baseline data collection

Baseline data collection will be undertaken at the participating site by an appropriately delegated member of the VESPER Trial team. Baseline data may be collected at the initial eligibility appointment or at a subsequent 'baseline' appointment (as described above).

- Demographics •
- **Registration form**
- Physical examination •
- Medical history •
- rUTI Impact questionnaire •
- UTI diary •
- EQ-5D-5L •
- Service use questionnaire •
- eGFR & LFTs (Blood samples) •
- Mid-steam urine samples
- Perineal swabs

Mid-stream urine samples and perineal swabs will be obtained and sent to the central laboratory.

13.1.3 Follow-up assessments

١. 1-month follow-up visit

One month following randomisation the following data and samples will be collected on CRFs. We will allow a time window of 1-month+3 weeks for this follow-up visit.

- rUTI Impact questionnaire
- UTI diary
- EQ-5D-5L
- Adherence to intervention form
- Adverse events
- GP or hospital records checked to confirm any additional urine culture results (outside of the scheduled hospital visits), including resistance patterns of the bacteria cultured
- eGFR & LFT bloods
- Mid-steam urine samples (central lab)

II. 3-months follow-up visit

Three months following randomisation the following data and samples will be collected on CRFs. We will allow a time window of 3-months +4 weeks for this follow-up visit.

- rUTI Impact questionnaire
- UTI diary
- EQ-5D-5L
- Adherence to intervention form
- Adverse events
- GP or hospital records checked to confirm any additional urine culture results (outside of the scheduled hospital visits), including resistance patterns of the bacteria cultured
- eGFR & LFT bloods
- Mid-steam urine samples (central lab)
- III. 6-months follow-up visit

Six months following randomisation the following data and samples will be collected on CRFs. We will allow a time window of 6-months +4 weeks for this follow-up visit.

• rUTI Impact questionnaire

UTI diary

Canolfan

- EQ-5D-5L
- Service use questionnaire
- **Treatment Satisfaction Questionnaire** •
- Adherence to intervention form •
- Adverse events •
- GP or hospital records checked to confirm any additional urine culture results (outside of the • scheduled hospital visits), including resistance patterns of the bacteria cultured
- eGFR & LFT bloods
- Mid-steam urine samples (central lab) •
- Perineal swab (Central lab)

IV. 12-month follow-up visit

Twelve months following randomisation the following data and samples will be collected on CRFs. We will allow a time window of 12-months +4 weeks for this follow-up visit.

- rUTI Impact questionnaire •
- UTI diary •
- EQ-5D-5L •
- Service use questionnaire
- Treatment Satisfaction Questionnaire •
- Adherence to intervention form •
- Adverse events •
- GP or hospital records checked to confirm any additional urine culture results (outside of the • scheduled hospital visits), including resistance patterns of the bacteria cultured
- eGFR & LFT bloods
- Mid-steam urine samples (central lab) •
- Perineal swab (Central lab)
- V. 13-month follow-up

Thirteen months following randomisation the following data will be collected, from all participants, on CRFs. We will allow a time window of 13-months +2 weeks for this follow-up visit.

• Discrete choice experiment

VI GP or hospital records search:

Data relevant to the trial including urine culture results (including resistance patterns of the isolated bacteria), antibiotic prescriptions, and health service utilisation will be extracted from the GP or hospital records for each participant for the 12-month period following randomisation.

13.1.4 Breakthrough UTIs – reporting of UTIs in periods between the follow-up visits

If a participant experiences symptoms of a UTI in the intervening periods between the clinic follow-up visits, they are requested to send a urine (and perineal sample only at months 6 &12) sample to the central laboratory before they take any prescribed discrete antibiotics to treat their UTI. They will also be asked to complete a UTI diary report form and rUTI impact questionnaire,

13.2 Qualitative process evaluation

13.2.1 Process evaluation

We will carry out a mixed methods process evaluation guided by the new MRC Framework²⁶ for developing and evaluating complex interventions to:

• understand acceptability and adherence to the intervention, and issues around implementation.

• explore participants' views on the trial processes including a qualitative overview of fidelity (e.g. local adaptations, contextual factors) and views on trial materials and processes (e.g. recruitment, consent and retention)

We will also look to identify an appropriate framework(s) to guide our qualitative data interpretation and analysis.

Interviews will be conducted via telephone or video call (depending on the preferences of the participant. We will give each participant a £10 voucher for their time spent participating in an interview.

13.2.2 Patient Interviews

VESPER Protocol V3.0_Approved_21.02.25

Canolfan

We will carry out semi-structured interviews remotely with around 20 women at two timepoints (total of around 40 interviews).

Interview 1: at the beginning of their involvement in the trial to explore how they have been managing their rUTI, and what their expectations of the trial and intervention are. We will use a purposive sample of women across both intervention trial arms (attempting to include women who have and have not self-administered) and control arm, and across sites. We will also attempt to include diversity across, ethnic groups and age to include experiences of women from under-represented groups.

Interview 2: towards the end of the trial/after follow-up to explore the same (where possible) participants' experiences of the intervention and trial, including the extent to which the intervention has fitted into their everyday lives, contextual factors which may have had an impact on this, and barriers and facilitators to implementation of the intervention. Where we are not able to carry out paired interviews (second interviews with the same women) we will recruit additional participants.

